9.4.3 ANALYSIS OF THE SECONDARY ENDPOINT(S)

Secondary outcomes of interest include: change in \log_{10} respiratory (nasopharyngeal swab, saliva RT-PCR) viral load from baseline (day 0) to days 2 and 6 post-randomization; \log_{10} and risk for a positive COVID-19 test at day 6, 14 and 28; and change of COVID-19 symptom score from baseline (day 0), as measured at days 6 and 14 +/- 2 days after enrollment (day 0). The same ANCOVA analysis as proposed for the primary endpoint will be used to analyze two and six day change in \log_{10} for the secondary endpoint. Risk for positive COVID19 test at day 6, 14 and 28 will be compared using an exact binomial distribution. Linear mixed models will be used to describe trajectories of change in the symptom score. The models will include fixed effects for treatment, time and the interaction of treatment and time. An unstructured covariance pattern will allow for correlation between repeated observations. Differences in means at each timepoint will be estimated along with 90% confidence intervals. All statistical tests will be conducted at 10% level of significance (two-sided) with no adjustment for multiple testing.

The COVID-19 PRO daily self score tool, derived almost entirely from a validated influenza symptom scoring. Tool (FLU-PRO)10 consists of 39 items that are answered daily. Items 1-33 are Likert scale questions (rated 0-4) where 0 = not at all, 1, 2 and 4 = very much. These items are summed to score the severity of symptoms- where a total score of 132 would indicate the greatest severity of symptoms and a score of 0 would indicate no severity of symptoms. Items 34-38 are also Likert scale questions (rated 0-4) that measure the frequency of specific daily symptoms where 0 = 0 times and 4 = 4 times or more. These items are summed to score the frequency of symptoms- where the highest score for the frequency of symptoms (20) indicates the greatest burden of symptom frequency. The last question (39) asks patients for their highest temperature in Fahrenheit.

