6.4 STUDY INTERVENTION COMPLIANCE

The study design is built around obtaining respiratory swabs and saliva from participants. To encourage compliance with study protocol, study drug/placebo will be provided every other day (prior to swabbing and saliva collection) and verbal assessment of whether study drug/placebo was taken as prescribed will be done.

Participants will have the option of not being swabbed again or providing saliva, even after receiving study drug, but lack of day 0 and 4 NP swabs would be a protocol deviation although they would be retained in intention to treat analysis. NP swabs are required at days 0, 4, 14, 28; optional swabs at days 2 and 6. Saliva will be collected at all study visits.

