9.2 SAMPLE SIZE DETERMINATION

The sample size calculation is based on the primary outcome of interest: change in \log_{10} respiratory (nasopharyngeal swab, saliva swab RT-PCR) viral load from baseline to day 4 post-randomization. Given the limited data on the variability of the change in \log_{10} viral load, we have powered the study based on detecting a moderate standardized effect size of 0.3 using an analysis of covariance (ANCOVA), adjusting for baseline \log_{10} viral load. To put into context, one scenario that would produce a 0.3 standardized effect size would be a change of 4 in \log_{10} viral load in the camostat mesylate group compared to a change of 1 in \log_{10} viral load in the placebo group assuming a standard deviation of 5.0. (NOTE: For ANCOVA, the effect size is the standard deviation of the treatment means divided by the pooled standard deviations of the observations.) To be conservative we assume a R-squared of 0 between the \log_{10} viral RNA at 4-days and baseline \log_{10} viral RNA. With a power of 90%, and a type I error rate of 10% (2-sided), we would be able to detect the hypothesized 0.3 standardized effect size with 98 total patients - 49 patients per group with a 1:1 randomization. Increasing this sample size by 15%, 5% for an efficacy and futility look at 50% information (i.e. when half of the patients have been enrolled) and 10% to account for loss to follow up, gives a total of 114 participants (57 per treatment arm).

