9.4.2 ANALYSIS OF THE PRIMARY EFFICACY ENDPOINT(S)

The primary analysis will be according to intent-to-treat and conducted using ANCOVA, adjusting for baseline \log_{10} viral load (or conversion from Ct value assuming $1 \log_{10} = 3.3$ Ct units). We will use the t-statistic for the treatment effect to determine whether the treatment is statistically different from the placebo at the overall 10% level of significance, controlling for baseline \log_{10} viral load. Because of the interim analysis (see below), a p-value of 0.06 (2-sided), corresponding to an efficacy boundary value of 1.875 at the last look, will be used for the level of significance for the primary outcome at the final analysis. In sensitivity analyses, we will also adjust for age and time since onset of symptoms. We will also conduct a per-protocol analysis as a secondary analysis. We will assess the missing mechanism and the impact of missing data. Sensitivity analyses under either missing at random or missing not at random will be considered, as appropriate.

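### Positivity at days 6, 14 and 28 is compared by an unnamed exact test without the baseline viral load already used elsewhere: two avoidable losses of power, neither a breach of the 10% level

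*Combined protocol and SAP*

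**What the plan says.** Section 9.4.3 (Analysis of the Secondary Endpoint(s)) sets the test for the three positivity endpoints: "Risk for positive COVID19 test at day 6, 14 and 28 will be compared using an exact binomial distribution". It does not say whether this means Fisher's conditional test or an unconditional exact test. It names no covariate, and it promises no effect estimate or interval for positivity, although the symptom-score differences in the same section get 90% confidence intervals. The level is fixed there too: "All statistical tests will be conducted at 10% level of significance (two-sided) with no adjustment for multiple testing".

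The continuous read-outs of the same assay are handled differently. For day 4, section 9.4.2 says: "The primary analysis will be according to intent-to-treat and conducted using ANCOVA, adjusting for baseline" log10 viral load. For days 2 and 6, section 9.4.3 says: "The same ANCOVA analysis as proposed for the primary endpoint will be used to analyze two and six day change in" log10 viral load.

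The baseline value should be on file for most participants. Section 6.4 states: "NP swabs are required at days 0, 4, 14, 28; optional swabs at days 2 and 6"; it also has saliva collected at every visit. The same section keeps participants who lack the day 0 and day 4 NP swabs in the intention-to-treat analysis, while counting this as a protocol deviation.

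**The concern.** Positivity is a dichotomised version of the result that is baseline-adjusted as a continuous measure, and the plan gives no reason for treating it differently. Section 4.2 says that viral burden differs between affected individuals by orders of magnitude, from 10^2 to 10^9 per swab. It is plausible that a participant who starts high is more likely to be still positive later. If so, raw proportions leave explainable variation in the comparison.

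The unnamed test is a second matter. Fisher's test is discrete and conservative at this sample size. The sponsor chose a 10% two-sided level without multiplicity adjustment, and Fisher's test would give back a good part of that allowance without the plan saying so. Leaving the test unnamed also leaves a choice that could be made after the data are seen.

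At stake is a missed reduction in the proportion still positive. Section 2.1 gives reduced transmission as part of the rationale, so this endpoint has some weight in reading the trial.

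**Working it through.** **Inputs from the documents.** Alpha 0.10 two-sided (9.4.3); 57 per arm randomised and 10% loss to follow-up (9.2), so 57 × 0.9 = 51.3, taken as 51 evaluable per arm.

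**Inputs not in the documents, so assumed.** Positivity of 70% v 50% and 50% v 30%; correlation ρ between baseline load and latent later load of 0, 0.3, 0.5 and 0.7. Section 9.2 says only: "To be conservative we assume a R-squared of 0 between the" day-4 and baseline log10 viral load. That is a planning assumption for the continuous outcome.

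**The plan's own figure.** No power is stated for positivity. The primary sample size reproduces: with f = 0.3 (a difference of 0.6 SD for two equal arms), alpha 0.10 and a noncentral F test with one numerator degree of freedom, power is 0.8985 at N = 96 and 0.904 at N = 98. Then 98 × 1.15 = 112.7, consistent with 114 (57 per arm) after rounding up.

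**Step 1: actual size of the exact test.** For a common rate p, size is the sum over all tables (x, y) of Bin(x; 51, p) × Bin(y; 51, p), counting only tables whose p-value is at most 0.10.

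- Fisher's test: about 6.5% at p = 0.3, 6.0% at 0.5 and 6.3% at 0.6; over 20 to 80% positive the range is 5.8 to 6.8%.
- Fisher's test at low rates (49 to 57 per arm): 4.8 to 5.4% at p = 0.10 and 2.2 to 2.8% at p = 0.05.
- Unconditional exact tests (Boschloo's or Z-ordered), which fit the wording equally well: about 8.7 to 10% over 20 to 80% positive.

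**Step 2: what discreteness costs.** Power uses the same sum with different rates in the two arms. The figures are the same for 70% v 50% and 50% v 30%, by symmetry.

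| Unadjusted test, 51 per arm | Power |
|---|---|
| Fisher | 58.4% |
| Boschloo | 64.9% |
| z test (chi-square) | 65.7% |

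Fisher against the z test: 65.7 − 58.4 = 7.3 points. Boschloo's test recovers 64.9 − 58.4 = 6.5 of these.

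**Step 3: what the covariate adds.** Latent later load is ρ × baseline + √(1 − ρ²) × noise, with positivity defined by a cut-off that gives the assumed rate in each arm. The test is the likelihood-ratio test for treatment in a logistic model with baseline load. Its critical value is recalibrated to a true 10% size, so that inflated size does not count as gain.

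| ρ (assumed) | Adjusted power, calibrated | Gain over unadjusted z (66%) |
|---|---|---|
| 0 | about 66% | about 0 |
| 0.3 | 67 to 68% | about 2 |
| 0.5 | 72 to 73% | about 7 |
| 0.7 | 80 to 81% | about 15 |

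Repeat simulations of this model gave 65 to 69% at ρ = 0.3. Against an unconditional exact test at about 65%, the gain there is between 0 and 4 points.

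**Step 4: a second parameterisation.** With a log-odds slope b per SD of baseline and 20-point differences between 80% and 20%, the uncalibrated adjusted test beats the unadjusted chi-square by 0 to 1 point at b = 0, 1 to 4 at b = 0.5, 5 to 9 at b = 1 and 11 to 14 at b = 1.5. The pattern is the same.

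**Step 5: size of the adjusted test.** Without calibration, the likelihood-ratio test ran at about 10 to 12%, with the highest values at 10% positivity.

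**Step 6: sparse outcomes.** For 10% v 3% positive, Fisher has 25% power, Boschloo 34% and the chi-square 46%. Over b = 0.5 to 1.5 the adjusted model adds only 2 to 6 points to the chi-square, before any correction for size. When few participants are positive, the choice of exact test matters more than the covariate.

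**The case against.** An unadjusted exact comparison of randomised arms is valid and controls type I error. These are secondary endpoints with no stated power target, and the viral-load endpoints already carry the baseline-adjusted evidence. All of that stands, and it makes this a point of efficiency and specification.

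Four stronger readings are tempting, and the documents do not support them.

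- A reader might add the two losses and say that omitting the covariate gives up 10 to 20 points. About 7 of those points come from the discreteness of Fisher's test, whatever covariate is used.
- A reader might take Fisher's test as the plan's choice. The wording fits an unconditional exact test equally well, and under that reading most of the first loss disappears.
- A reader might call a test running near 6% a departure from the stated 10% level. A size below nominal is conservative and keeps within the limit.
- A reader might take the 10^2 to 10^9 range in section 4.2 as proof that baseline load predicts later positivity. It describes spread among affected individuals. It is not given as a day-0 range, and spread is not prognostic strength. No passage gives the association or any positivity rate.

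The remedy also has costs. A complete-case logistic model would drop participants without a baseline value, whom section 6.4 retains and a raw comparison keeps. The plan names two specimen types and does not say which baseline would be the covariate. Day 6 NP swabs are optional, so 51 per arm is uncertain there if positivity is NP-based. These objections shape the fix but do not remove the case for it: with no prognostic value at all, the adjusted test performed within simulation noise of the unadjusted z test.

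**Conclusion.** The point holds as a cheap improvement with two separate parts. The unnamed exact test and the missing covariate are matters of text and are certain. The actual size of Fisher's test is also firm, but it applies only if Fisher's test is what the plan means. The power figures are conditional: about 7 points for choosing Fisher's test, plus about 0, 2, 7 or 15 points for the covariate at assumed correlations of 0, 0.3, 0.5 or 0.7. They rest on 51 evaluable per arm and mid-range positivity with a 20-point difference. They should not be carried over to day 28 if few participants are then positive.

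A reader might conclude that the positivity analysis is wrong or that its error rate is misstated. Neither follows: the planned comparison is valid, and no stated figure in the plan is contradicted.

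**What to change.** In section 9.4.3:

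1. Analyse positivity at each of days 6, 14 and 28 by logistic regression with treatment and baseline log10 viral load, taking the baseline from the same specimen type (NP swab or saliva) as the outcome.
2. Report the standardised (marginal) risk difference with a 90% confidence interval, and state which statistic supplies the p-value. Show the raw proportions alongside.
3. Keep participants with a missing baseline value by a pre-stated method, for example a missing indicator or mean imputation of the baseline covariate.
4. Where one outcome category is sparse, probably at day 28, use a Firth-penalised fit or a named unconditional exact test such as Boschloo's. Fix the rule for choosing between them before unblinding.

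If the sponsor prefers to stay unadjusted, naming an unconditional exact test recovers most of the first loss and closes the post hoc choice.

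Cost: no new data, since the covariate is already collected and already used in the ANCOVA. There is slightly more analysis work, rules are needed for specimen type, missing baselines and sparse days, and the likelihood-ratio test runs at about 10 to 12% rather than being guaranteed at or below 10%.

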1.3 SCHEDULE OF ACTIVITIES (SOA)

Procedures	Enrollment, Study Visit 1, Day 0	Study Visit 2 Day 2	Study Visit 3 Day 4	Study Visit 4 Day 6	Study Visit 5 Day 14+/- 2 days	Study Visit 6 Day 28+/- 2 days
Informed consent	X					
Demographics	X					
Medical history	X					
Randomization	X					
Administer study intervention: Subjects receive two days worth of drug/placebo on days 0, 2, 4 and one day of drug/placebo on day 6	X Drug/placebo For 2 days	X Drug/placebo For 2 days	X Drug/placebo For 2 days	X Drug/placebo For 1 day		
Nasopharyngeal swabs, saliva for COVID-19 RT-PCR and antigen testing	X	X Swabs optional	X	X Swabs optional	X	X
Physical exam: Vital signs, wt, pulse oximetry, other as clinically indicated	X	X	X	X	X	X
Urine pregnancy test (as indicated)	X					
Blood pregnancy test (as indicated)					X	
Hematology and coagulation	X				X	X
Blood chemistries	X				X	X
Adverse event review and evaluation	X	X	X	X	X	X
Concomitant medication review	X	X	X	X	X	X
Blood for research biorepository	X				X	X
Complete Case Report Forms (CRFs)	X	X	X	X	X	X

All subjects, regardless of study arm (blinded to subjects and investigators), will be tracked for their health status through daily phone calls from days 0 to day 14 with routine, scheduled daily phone calls by study staff to help participants fill out symptom scores on the standardized COVID-19-PRO instrument. Any subject reporting concerning symptoms, particularly chest pain, shortness of breath, extreme prostration, change in mental status will be referred to for emergency care. Subjects will be given a contact phone number of PI or designee to contact for any concerns. If there is complete resolution of symptoms at the day 14 visit, then phone calls will not be routinely continued by our study staff but subjects will be encouraged to call PI or designee for concerns or discussions.

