6.1.2 DOSING AND ADMINISTRATION

Camostat mesylate 200 mg po qid vs. placebo for 7 days.

Two days of study drug or placebo will be provided every other day in the study clinic at the time of check-in, prior to being swabbed and obtaining saliva samples.

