9 STATISTICAL CONSIDERATIONS

9.1 STATISTICAL HYPOTHESES

All tests performed will be tests of superiority.

For the primary endpoint, we will test the hypothesis that camostat mesylate results in a significantly greater change from baseline to day 4 in respiratory (Nasopharyngeal swab, saliva RT-PCR) \log_{10} viral load compared to placebo.

Similarly, for secondary endpoints we will test the hypothesis that camostat mesylate will result in a significantly greater change from baseline to days 2 and 6 in respiratory (nasopharyngeal swab, saliva RT-PCR) \log_{10} viral load compared to placebo; that camostat mesylate will reduce \log_{10} of a positive COVID19 test at days 2 and 6 (optional swabs), rate of positive tests at days 6, 14 (required), and 28 (required); and that camostat mesylate will result in lower symptom burden at days 6 and 14.

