9.4 STATISTICAL ANALYSES

9.4.1 GENERAL APPROACH

All primary analyses will be performed as intent-to-treat analyses with a type I error rate of 10% (two-sided). Parametric distributional assumptions will be checked. If assumptions fail, other distributions will be considered prior to transformations and non-parametric methods. SAS (version 9.4) or the latest version of R (currently 3.6.3) will be used to analyze the data.

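### The symptom-score mixed model makes no use of the day-0 score to sharpen the treatment comparison, unlike the viral-load ANCOVAs: avoidable loss of precision in a secondary endpoint

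*Combined protocol and SAP*

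**What the plan says.** Section 9.4.3 lists the symptom score among the secondary endpoints as a change from day 0 to days 6 and 14. Its model is a linear mixed model with an unstructured covariance. The fixed effects are given in full: "The models will include fixed effects for treatment, time and the interaction of treatment and time". The output is described as follows: "Differences in means at each timepoint will be estimated along with 90% confidence intervals". Section 9.1 words the hypothesis as "camostat mesylate will result in lower symptom burden at days 6 and 14". The plan does not say whether the response is the score itself (with day 0 among the responses) or the change from day 0.

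Viral load is handled differently. Section 9.4.2 states: "The primary analysis will be according to intent-to-treat and conducted using ANCOVA, adjusting for baseline" log10 viral load. Section 9.4.3 extends this to days 2 and 6: "The same ANCOVA analysis as proposed for the primary endpoint will be used to analyze two and six day change in" log10 viral load.

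Section 1.3 describes how symptom scores are collected: "daily phone calls from days 0 to day 14 with routine, scheduled daily phone calls by study staff to help participants fill out symptom scores". A day-0 score is therefore already planned.

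**The concern.** Among the primary and secondary endpoints, the symptom score is the only continuous change-from-baseline measure without baseline adjustment, and no reason is given.

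The planned contrast can be read as a difference in raw visit means or as a difference in mean change. Unless r is close to zero, the first reading is less precise than a baseline-adjusted comparison; the second is less precise at every r below 1 when the SDs are equal. What is at stake is the width of the day-6 and day-14 confidence intervals.

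This is not wholly academic. Section 2.1 and the primary row of the Section 3 table rest further development on viral load. The secondary row of that table, however, says that a further trial would lack justification if the secondary endpoints are missed.

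**Working it through.** **Inputs from the documents.** Fixed effects, unstructured covariance and two-sided 10% level: Section 9.4.3. 57 per arm and 10% loss to follow-up: Section 9.2, giving 57 × 0.9 = 51.3, taken as 51 per arm.

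**Assumptions (no figure in the documents).** Baseline/follow-up correlation r = 0.3, 0.5, 0.7; ratio k of follow-up SD to baseline SD, 1 unless stated; effect 0.5 follow-up SD; day-6/day-14 correlation 0.6.

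**The plan's own figure.** There is none for the symptom score. Section 9.2 sizes the trial on viral load alone, and that figure reproduces: d = 3/5 = 0.6 with 49 per arm gives 90.4% power (noncentral t), and 98 × 1.15 = 112.7, rounded up to 114.

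**Step 1: variance of the treatment difference at one visit.** With n per arm and follow-up SD σ:

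- raw means: 2σ²/n
- change scores: (2σ²/n)(1 + 1/k² − 2r/k), which is (2σ²/n) × 2(1 − r) at k = 1
- baseline-adjusted: (2σ²/n)(1 − r²)

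So adjusted/raw = 1 − r². Adjusted/change = k²(1 − r²)/(1 + k² − 2rk), which is (1 + r)/2 at k = 1.

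| | r = 0.3 | r = 0.5 | r = 0.7 |
|---|---|---|---|
| adjusted/raw variance | 0.91 | 0.75 | 0.51 |
| extra patients raw means need to match | 10% | 33% | 96% |
| adjusted/change variance (k = 1) | 0.65 | 0.75 | 0.85 |
| extra patients change scores need to match | 54% | 33% | 18% |

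At r = 0.5 the unadjusted standard error is 1/√0.75 = 1.155 times the adjusted one under either reading.

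**Step 2: does the unstructured covariance recover this?** Generalised least squares variances were computed for days 0, 6 and 14 with 57 per arm. With a separate day-0 mean in each arm and complete data, the day-14 variance is exactly that of the raw mean or the change score. Constraining the day-0 means to be equal gives the adjusted ratios above. Using day 0 as a covariate gives the same variance as the constraint. With 10% missing at day 14 the ratios are 0.92/0.77/0.54 (raw) and 0.67/0.77/0.86 (change).

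**Step 3: power.** Noncentral t, 51 per arm, two-sided alpha 0.10. Unadjusted analyses have 100 df; the adjusted analysis has 99 df and a variance factor of 1 + 1/98.

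| | r = 0.3 | r = 0.5 | r = 0.7 |
|---|---|---|---|
| raw means | 81% | 81% | 81% |
| change, k = 1 | 68% | 81% | 94% |
| change, k = 0.5 | 36% | 42% | 52% |
| adjusted | 83% | 89% | 97% |

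At r = 0 the adjusted analysis has 80.2% against 80.6% for raw means, and the two break even near r = 0.1. A smaller follow-up SD enlarges the loss only under the change-score reading.

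**Step 4: validity.** Trials with no effect were simulated (57 per arm, 6,000 runs per setting, alpha 0.10).

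- Complete data: rejection 0.095 to 0.104 for raw, change and adjusted analyses alike.
- About 10% dropout depending on the day-0 score in the same way in both arms: 0.095 to 0.107 unadjusted.
- Dropout depending on the day-0 score in opposite directions by arm (an extreme assumed case), with no day-0 response in the model: 0.11 to 0.18 unadjusted, about 0.10 adjusted.

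**The case against.** The planned model is a standard, valid longitudinal analysis of an endpoint on which the trial was not sized, and Section 9.4.3 uses it to describe trajectories. Every input that fixes the size of the loss is assumed. At r = 0.3 under the raw-mean reading the gain is about 3 points of power, and at r of about 0.1 or less there is none. All of this stands. It limits the importance of the point, but it gives no reason to leave out a score that is already collected: the worst case is the loss of one degree of freedom.

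Symptom scores will also pile up at zero as patients recover. A floor check used 20,000 simulated trials per cell, with scores rounded and bounded at 0 and 132, assumed baseline mean 35 and SD 20, and a latent day-14 effect of 10 points. At r = 0.5 the gain over raw means fell from 9 points of power with no floor to 8, 7 and 4 points with 30%, 50% and 70% of placebo patients at zero. It shrank but did not reverse. These figures are for linear models. Section 9.4.1 says "If assumptions fail, other distributions will be considered prior to transformations and non-parametric methods", and they need not carry over to such models.

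A reader might infer that the symptom comparison is biased. The documents do not support that. Randomisation protects it with complete data, or with day 0 in the response under missing at random. The raised error rates need both a model without day 0 and dropout that runs in opposite directions in the two arms, which nothing in the plan suggests.

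**Conclusion.** The point holds as an avoidable loss of precision. At r between 0.3 and 0.7 with equal SDs, adjustment would reduce the variance by 9% to 49% relative to raw means, or by 35% to 15% relative to change scores. Which reading applies, and what r is, cannot be settled from the documents. The advantage over change scores grows if the follow-up SD is smaller than the baseline SD; the advantage over raw means disappears as r falls to about 0.1.

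Two stronger conclusions should not be drawn. The omission does not touch the primary analysis or N = 114. Nor does it decide the development question by itself: Section 2.1 and the primary row in Section 3 rest on viral load. But the secondary row in Section 3 makes the secondary endpoints count, so the precision of this comparison bears on a stated decision.

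**What to change.** In Section 9.4.3, choose one of two forms:

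- **(a)** Post-baseline scores as the response, with the day-0 score and its interaction with time added as fixed effects. For the planned comparison the timepoints are days 6 and 14.
- **(b)** Day 0 kept in the response, with the arm means constrained equal at day 0. The timepoints are days 0, 6 and 14. This form also retains participants who have no day-0 score.

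Under either, report the day-6 and day-14 treatment differences with 90% confidence intervals. The daily scores can still be used separately to describe trajectories.

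Specify that the day-0 score is the one recorded before the first dose. The documents do not give this order: scores are taken by phone call, while study drug or placebo "will be provided every other day in the study clinic at the time of check-in, prior to being swabbed". If treatment had already moved the day-0 score by an assumed 0.1 SD, adjustment would attenuate the difference by r × 0.1 = 0.03, 0.05 or 0.07 SD, and a change score would attenuate it by the full 0.1 SD.

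The cost is SAP wording, plus one CRF instruction if the pre-dose order is not already assured. Form (a) adds two parameters; form (b) has one fewer than a model with free day-0 means. No visits, samples or patients are added.
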